2.1 Device description

Saypha® FILLER Lidocaine is conceived for medical purposes and aims to address reconstructive purposes in the treatment, for instance, of facial lipoatrophy, debilitating scars or morphological asymmetry and increase lip volume. The device received the CE mark in 2016 allowing device sales in European Union (EU). The chemical, physical and biological properties of Saypha® FILLER Lidocaine were extensively characterized during development (see sections 4 and 5 of the IB¹¹ for details). Compliance with general requirements defined in EN ISO 14630^A was demonstrated.

Saypha® FILLER Lidocaine was classified as an implantable medical device in permanent contact with tissues or bones according to EN ISO 10993-1^B. Hence, cytotoxicity, acute, repeated dose and subchronic systemic toxicity, local effects after implantation, sensitization, irritation, pyrogenicity and genotoxicity of Saypha® Filler Lidocaine were evaluated *in vitro* and *in vivo* in biocompatibility studies. All of the studies were conducted under GLP^C principles and results are described in section 5.1 of the IB.

Table 2 shows the components and main characteristics of Saypha® Filler Lidocaine and Table 3 tabulates the single components of Saypha® Filler Lidocaine.

^A EN ISO 14630: Non-active surgical implants — General requirements

EN ISO 10993-1: Biological evaluation of medical devices — Part 1: Evaluation and testing

^C GLP: Good Laboratory Practice

Table 2. Main Characteristics of Saypha® Filler Lidocaine

Components of Saypha® Filler Lidocaine

- 23 mg/mLin a physiologic buffer (phosphate buffer pH 6.7–7.3 q.s., sodium chloride)
- 3 mg/g [0.3%] lidocaine hydrochloride

Description of Saypha® FILLER Lidocaine

- is a class III medical device incorporating the ancillary medicinal substance lidocaine hydrochloride as an integral part
- is a sterile, biodegradable, viscoelastic, clear, isotonic and homogenized injectable gel implant (pre-filled in 1 mL glass syringes)
- is designed for single use and must not be re-sterilized
- has an anticipated lifetime up to nine months after treatment

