4.1 Anticipated clinical benefits

The treatment with Saypha® FILLER Lidocaine may remove or reduce a distressing aesthetic defect in subjects with volume deficiency of lips ("very thin" lip shows to "moderately thick" lip shows, see section 6.4.7), thereby improving their psychological and social wellbeing. This is achieved by a minimally invasive procedure with a short downtime, which results in an immediate and long-lasting effect anticipated to last up to nine months after treatment.

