6.4.12 Assessment of aesthetic effect

At each follow-up visit, the investigator will evaluate the aesthetic effect. The presence of an aesthetic effect at a given visit relative to baseline will be recorded as either "YES" or "NO" in the subject's medical record and in the eCRF.

The duration of the clinical investigation is planned for 18 months at a maximum and depends on the assessment of the aesthetic effect. In case it is observed by the investigator that no aesthetic effect is any more visible the study can be terminated at Month 12 (Visit 5) for the respective subject.

If no aesthetic effect is present anymore new injections for lip augmentation might be placed at previously injected locations after 3 months in general.

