6.5.3 Visit 2 – Week 3 (after Visit 1) ± 2 days

- Record any new AE or changes of AEs (see section 14) with special focus on inflammatory reactions persisting for more than one week or any other occurring secondary effect (see section 6.4.13).
- Record changes in concomitant medication and procedures (see section 6.4.3)

Optional Touch-up IMD administration (see Section 6.2):

The touch-up treatment is optional and will be conducted at investigator's discretion, if full correction was not achieved after initial IMD treatment (i.e., at Visit 1). If the investigator decides to conduct a touch-up treatment, the following assessments must be conducted for the respective subjects:

- Document information on injection (see section 6.4.6)
- Place the one peel-off label of the outer carton box in the subject's medical record (see section 2.5)
- Pain assessment (during treatment) using the NPRS by subject immediately after IMD administration (see section 6.4.8)
- Pain assessment (during recovery from treatment) using the NPRS by subject 15 min after administration of the IMD (see section 6.4.8)
- The subject should be kept at the investigation site and observed for at least 15 min after IMD administration in order to identify potential AEs post-administration
- Re-advise the subject prior to discharge to follow restrictions specified in section 6.3.7 and to
 inform the investigator especially about inflammatory reactions persisting for more than one week
 or any other occurring secondary effect (see section 6.4.13).
- Record any device deficiencies (see section 14.8)

6.5.4 Visit 2a - Telephone Visit - Day 1 (24h after touch-up) – only in case of touch-up treatment

- Ask for any changes in AEs and new AEs (see section 14)
- Ask for changes in concomitant medication and procedures (see section 6.4.3)

In case of an AE an unscheduled on-site visit should be performed (see section 6.5.7).

6.5.5 Visit 3 to 6 – Week 6 to Month 18 (after Visit 1)

Through the follow-up phase of the investigation the following visits will be performed:

- Visit 3 Week 6 (± 5 d) after Visit 1
- Visit 4 Month 6 / Week 26 (± 7 d) after Visit 1
- Visit 5 Month 12 / Week 52 (± 7 d) after Visit 1
- Visit 6 Month 18 / Week 76 (± 7 d) after Visit 1 optional

The following assessment will be performed through these follow-up visits:

- Record any new AE or changes of AEs (see section 14)

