7.1.1 Main Objectives

1. To evaluate the effectiveness, safety and long-term safety of Saypha® FILLER Lidocaine for lip augmentation;
2. To assess the duration of the aesthetic effect of Saypha® FILLER Lidocaine for lip augmentation

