8.2.2 Secondary Performance Endpoint

1. The percentage of responders, based on the investigator live assessment at 6, 12 and optional 18 months after the initial treatment using the validated LFS.
2. The percentage of responders based on the independent photographic reviewer's assessments before initial treatment and at Week 6, Month 6, 12 and optional Month 18 after initial treatment, based on photographs and using the validated LFS.
3. The percentage of subjects with an improvement relative to baseline photographs, (subjects who have been rated as "very much improved" or "much improved" or "improved"), based on the investigator assessment at Week 6, Month 6, 12 and optional Month 18 after initial treatment using the 5-point GAIS.
4. The percentage of subjects with an improvement relative to baseline photographs (subjects who have been rated as "very much improved" or "much improved" or "improved"), based on subject assessment at Week 6, Month 6, 12 and optional Month 18 after initial treatment, using the 5-point GAIS.
5. The extent of subject's satisfaction with overall outcome of the treatment, at Week 6, Month 6, 12 and optional Month 18 after initial treatment, assessed by the subject using the Face-Q™ Questionnaire "Satisfaction with Outcome".
6. The extent of subject's satisfaction with augmentation of lips, at Week 6, Month 6, 12 and optional Month 18 after initial treatment, assessed by the subject using the Face-Q™ Questionnaire "Satisfaction with Lips".
7. Subject's perception of pain after initial and touch-up treatment with Saypha® FILLER Lidocaine using the 11-point Numeric Pain Rating Scale (NPRS), where 0 is no pain and 10 is the worst pain imaginable.
8. Percentage of subjects demonstrating an aesthetic effect at Week 6, Month 6, 12 and optional Month 18 based on the investigator's life assessment.
9. Injection volume (initial and touch-up) required for an optimal augmentation of the lips with Saypha® FILLER Lidocaine

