The extent of subject's satisfaction with overall outcome of the treatment, at Week 6, Month 6, 12 and optional Month 18 after initial treatment, assessed by the subject using the Face-Q™ Questionnaire "Satisfaction with Outcome" for each question will be summarized by number and percentage using PPS and FAS population.

Face Q data will be analyzed according to the FaceQ USER'S GUIDE (VERSION 1.0 January 2015). The raw summed scale score is converted to a score from 0 to 100 by using the respective Conversion Tables available from the authors. Higher scores reflect a better outcome (i.e., 0 (worst) to 100 (best)).

Listings will be provided for Face-Q™ Questionnaire "Satisfaction with Outcome".

6. The extent of subject's satisfaction with augmentation of lips, at Week 6, Month 6, 12 and optional Month 18 after initial treatment, assessed by the subject using the Face-Q™ Questionnaire "Satisfaction with Lips".

The extent of subject's satisfaction with augmentation of lips, at Week 6, Month 6, 12 and optional Month 18 after initial treatment, assessed by the subject using the Face-Q™ Questionnaire "Satisfaction with Lips" for each question will be summarized by number and percentage using PPS and FAS population.

Listings will be provided for Face-Q™ Questionnaire "Satisfaction with Lips".

7. Subject's perception of pain after initial and touch-up treatment with Saypha® FILLER Lidocaine using the 11-point Numeric Pain Rating Scale (NPRS), where 0 is no pain and 10 is the worst pain imaginable.

Subject's perception of pain after initial and touch-up treatment with Saypha® FILLER Lidocaine using the 11-point Numeric Pain Rating Scale (NPRS) will be analyzed descriptively using PPS and FAS populations.

Paired t-test will be performed to check the mean difference between "immediately after" and "15 minutes later at each visit are significant at 5% level of significance.

Listings will be provided for Numeric Pain Rating Scale (NPRS).

8. Percentage of subjects demonstrating an aesthetic effect at Week 6, Month 6, 12 and optional Month 18 based on the investigator's life assessment.

Percentage of subjects demonstrating an aesthetic effect at Week 6, Month 6, 12 and optional Month 18 based on the investigator's life assessment will be summarized by number and percentage using PPS and FAS population.

	Statistical Analysis Plan Sponsor: CROMA-PHARMA GmbH
	Study Number: CPH-101-201479 Version: Final 1.0 Date: 07 Jun 2021

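### Duration of the aesthetic effect is a main objective, but the SAP plans only visit percentages with no duration estimate, and the Month 18 percentage may rest on a selected group

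*SAP*

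**What the plan says.** SAP 7.1.1, repeating protocol 5.1, lists as the second main objective: "To assess the duration of the aesthetic effect of Saypha® FILLER Lidocaine for lip augmentation". Protocol 6.4.12 describes the measurement: "The presence of an aesthetic effect at a given visit relative to baseline will be recorded as either" YES or NO. No date of loss is described. The endpoint in SAP 8.2.2 is "Percentage of subjects demonstrating an aesthetic effect at Week 6, Month 6, 12 and optional Month 18". For its analysis, SAP 10.6.2 item 8 says that the percentage based on the investigator's "life assessment will be summarized by number and percentage using PPS and FAS population". The derived-variable table in SAP 9.3 contains no duration of effect, and neither document mentions a median duration, a time to loss or an interval-censored method.

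The protocol states an expectation twice. Table 2 in section 2.1 says the device "has an anticipated lifetime up to nine months after treatment", and section 4.1 speaks of a "long-lasting effect anticipated to last up to nine months after treatment". Protocol 6.5.5 schedules "Visit 4 Month 6 / Week 26 (± 7 d) after Visit 1" and then "Visit 5 Month 12 / Week 52 (± 7 d) after Visit 1", with nothing between.

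Protocol 6.4.12 and 6.5.5 allow participation to end at Month 12 when the investigator no longer sees an effect; otherwise a Month 18 visit should be scheduled. Protocol 7.5 rules out imputing missing values, and the effectiveness imputation in SAP 9.5.1 covers only the FACE-Q items.

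**The concern.** A main objective should lead to a defined quantity and a method for estimating it. Here the reader receives up to four separate percentages and must turn them into a duration unaided. Two things are at stake.

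- **No stated duration.** If the share with an effect is above one half at Month 6 and below one half at Month 12, the table places the median somewhere in a 26-week interval. Nine months lies in the middle of it. Without a statement in the SAP, such a result could be presented as agreeing with nine months, although it agrees equally well with any other time in the interval.
- **The Month 18 figure.** Whether a subject is seen at Month 18 depends on the Month 12 rating. If the percentage is taken among those assessed, the subjects most likely to be NO have been removed from the denominator.

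**Working it through.** **The plan's own precision figure.** SAP 9.6 gives 95% half-widths for the Week 6 responder rate with p = 0.900. The formula is 1.96 × √(p(1 − p)/n).
- n = 100: 1.96 × √(0.09/100) = 0.0588, stated as 0.059.
- n = 50: 1.96 × √(0.09/50) = 0.0832, stated as 0.083.

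Both reproduce. They concern Week 6 response; no precision is stated for duration.

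**Where nine months falls.** The scheduled weeks are 6, 26, 52 and 76, so the gaps are 20, 26 and 24 weeks. With the ±7-day windows, the middle gap is 24 to 28 weeks. Nine months is 9 × 365.25/12/7 = 39.1 weeks, and the midpoint of the gap is (26 + 52)/2 = 39 weeks. LFS, GAIS and FACE-Q follow the same visits and do not fill it. Unscheduled visits do not either, because SAP 9.5.2 bases summaries on scheduled time points.

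**What the percentages can and cannot show.** The documents give no distribution of loss times, so a Weibull with median m weeks and shape k is assumed for illustration. The share still showing an effect at week t is S(t) = 0.5^((t/m)^k). With k = 3:

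| Median | Week 26 | Week 52 |
|---|---|---|
| 28.3 weeks (6.5 months) | about 58% | about 1% |
| 39 weeks | 81.4% | 19.3% |
| 48 weeks | 89.6% | 41.4% |
| 50 weeks (11.5 months) | about 91% | about 46% |

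The first and last rows differ by far more than sampling error: at n = 100 the widest possible half-width is 1.96 × √(0.25/100) = 0.098. All four rows nevertheless cross 50% between Weeks 26 and 52, so without a distributional assumption each yields the same bracket for the median.

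**The Month 18 denominator.** Take k = 2 and m = 39, with every subject lacking an effect at Month 12 leaving and every other subject attending Month 18.
- S(52) = 0.5^((52/39)²) = 0.5^1.778 = 0.292
- S(76) = 0.5^((76/39)²) = 0.5^3.797 = 0.072
- Among those with an effect at Month 12: 0.072/0.292 = 24.7%
- Among all subjects: 7.2%

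The ratio is 1/0.292, about 3.4. With k = 3 and m = 48 the two figures are 15.4% and 6.4%. The size depends on the assumption. The direction does not, provided that those who leave are the ones without an effect.

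**What an interval-censored curve adds.** With common visits, no return of effect and complete data, the Turnbull estimate at Weeks 6, 26 and 52 equals the planned percentages. It differs once subjects drop out or leave at Month 12, because a subject whose first NO is at Month 12 stays in the estimate as a loss between Weeks 26 and 52.

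**The case against.** The best defence is that the study is descriptive (protocol 5.2, SAP 9.8), that the objective is to assess duration, and that persistence is reported at fixed times by several measures: investigator and photographic LFS, two GAIS ratings and the aesthetic effect. Protocol 7.3 also plans confidence intervals for responder percentages over time. This stands: the objective is addressed, though coarsely. It does not supply a duration, and a Turnbull curve is itself descriptive.

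A second defence concerns the denominator. SAP 9.1 shows percentages relative to N, the number of subjects in a group. If that means the whole FAS at every visit, Month 12 exits already count as not YES. But the SAP does not say whether the group at Month 18 is the FAS or those assessed, and a full-FAS denominator would treat ordinary dropouts as losses too. The ambiguity remains.

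Several stronger readings are tempting and should not be drawn.
- *The table cannot tell a 6.5-month product from an 11.5-month one.* That holds only if losses cluster inside the gap. The table above shows clear separation when they are spread.
- *Loss at 27, 39 or 51 weeks gives the same result, so the analysis is at fault.* If all subjects lost the effect at one of those times, the visits would look identical. That comes from the schedule, and a Turnbull curve on the same visits would not change it.
- *Duration will be overstated by up to 26 weeks, or 13 on average.* This would follow from dating each loss at the visit where it is first seen. Neither document plans that, so these are not errors in the planned output.
- *The results can say nothing about nine months.* The wording is up to nine months, so substantial persistence at Month 12 would speak against it. Protocol 5.3 does not list nine months among the claims to be verified.
- *Counting from initial treatment is wrong because of the Week 3 touch-up.* Endpoint times are consistently defined from initial treatment. The choice of origin is a preference.

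**Conclusion.** The point holds in a limited form. A main objective has no defined duration variable and no estimator, and a median between Weeks 26 and 52 can only be bracketed. That follows directly from the documents. The planned percentages remain informative about persistence at each visit.

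The part that can change a reported number is Month 18: 24.7% against 7.2% in the worked case. This rests on an assumed Weibull loss (shape 2, median 39 weeks), on all subjects without an effect leaving at Month 12, on no other dropout, and on the percentage being taken among those assessed. The protocol permits the exit without requiring it, so the selection may be partial. The change is a worthwhile, inexpensive improvement and does not call the design into question.

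**What to change.** In SAP 10.6.2 item 8:

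1. Define a per-subject time to loss of aesthetic effect from initial treatment. Make it interval-censored between the last YES and the first NO visit, and right-censored at the last visit if still YES.
2. State the rules for NO followed by YES and for subjects never rated YES.
3. Summarise it descriptively in the FAS with a nonparametric interval-censored (Turnbull) curve, and report the median as an interval.
4. State that a bracket from Week 26 to Week 52 does not confirm nine months.
5. For the Month 18 percentage, count subjects who exited at Month 12 for loss of effect as NO, or state the denominator and show both versions.
6. If wanted, give time from last injection as a supportive version only.

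The cost is some SAP wording, one derived variable and one curve, all from data already collected and with no added visit. The drawback is that duration appears as a wide bracket and not as a single figure. A parametric fit would look more precise, but only by assuming a shape that the documents do not give.

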6.1 Design description

This is a prospective, open-label, multicentre, randomized investigation to evaluate the effectiveness, safety and long-term safety of Saypha® FILLER Lidocaine for bilateral lip augmentation and to assess the duration of the aesthetic effect of the device. As justified in section 3.3, this type of design is considered appropriate in view of the purpose and objectives of the study.

The investigation comprises of six on-site visits within 18 months (76 weeks):the Screening/Baseline visit (Visit 1/Day 0) and 5 follow-up visits at 3 weeks (Visit 2), 6 weeks (Visit 3), 6, 12, and 18 months after initial treatment (Visits 4, 5 and 6). Visit 6 at Month 18 is an optional visit. In case it is observed by the investigator at the 12 months visit (Visit 5) that no aesthetic effect is any more visible the study can be terminated at Visit 5. Subjects will randomly be assigned to one of the two IMDs at a 1:1 ratio ('IMD-HQ': 'IMD-C1').

The Screening/Baseline visit (Visit 1) will entail informed consent and screening assessments as specified in section 6.5.1. During this visit the investigator will determine the inclusion of subjects based on inclusion/exclusion criteria (see sections 6.3.3 and 6.3.4).

Eligible subjects will be randomized to one of the IMDs ('IMD-HQ' or 'IMD-C1') and undergo bilateral lip augmentation treatment with Saypha® FILLER Lidocaine in order to correct moderate to severe deficiency of lip volume at Visit 1 (Day 0). In addition to this initial treatment an optional touch-up treatment can be performed at Visit 2 (Week 3) in order to achieve optimal cosmetic corrections (in the discretion of the investigator). The injection volume will be recorded at each treatment visit (i.e., Visit 1 and Visit 2) (see section 6.4.6). 24 hours after each treatment a telephone visit will be performed for safety evaluation (Visit 1a and Visit 2a in case of touch-up treatment; see sections 6.5.2 and 6.5.4).

Baseline severity of lip volume deficiency will be determined at Visit 1 by the investigator using a validated 5-point Lip Fullness Scale (LFS) before the initial treatment. The LFS will be repeated 6 weeks and 6, 12 and optional 18 months after the initial IMD treatment. Independent photographic reviews will be performed at the same time points using LFS on photographs (see section 6.4.7).

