6.2 Investigational medical device (IMD)

6.2.1 Packaging, labelling and storage

Each device will be provided in a folding box containing one glass syringe prefilled with 1.0 mL of the injectable gel implant and two 27G $\frac{1}{2}$ " disposable sterile needles, and a product leaflet (Instructions for Use; IFU¹⁶). Additionally, cannulas (25G x 50mm and 22G x 70mm) will be provided.

Two labels showing the batch number are attached to the boxes. One of these should be attached to the subject's medical record. IMDs from the two different manufacturing sites (see section 2.2) can separately be identified and differentiated by investigator. The IMD is labeled according to applicable guidelines and national legal requirements indicating that the device is exclusively for use in a clinical investigation.

The IMD must be stored in the original box, at 2-25°C (36-77 °F) in a dry place, protected from light, heat and frost. The shelf life of finished sterilized Saypha® FILLER Lidocaine is 24 months at the specified storage conditions.

The investigator must ensure that upon receipt of the IMD and other study supplies, these are kept in an appropriate and secure location, with access limited to authorized individuals.

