7.1.2 Additional Objectives

1. To compare the effectiveness of Saypha® FILLER Lidocaine ('IMD-HQ' and 'IMD-C1') produced in the two different manufacturing sites ('HQ' and 'C1').
2. To compare the IMD injection techniques: 'retrograde technique' and 'bolus technique'
3. To compare the injection equipment used: '27G ½" needle' versus cannula ('25G x 50mm cannula' or '22G x 70mm cannula')

8 Study Design

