8.1.2 Treatment Regimen

Saypha® FILLER Lidocaine is a sterile, biodegradable, viscoelastic, transparent, isotonic and homogenized injectable gel implant formulated in a physiologic buffer to a concentration of 23 mg/mL, with addition of 3 mg/mL (0.3%) lidocaine hydrochloride. Saypha® FILLER Lidocaine is administered by injection into the lips. The volume applied depends on the size of the area which requires correction and will be selected by the investigator. A maximum volume of 2 mL for both lips in total (i.e., for upper plus lower lip) including touch up might be needed per treatment but the treatment should not exceed 10 mL in total per treatment or 20 mL per year.

The manufacturing process of Saypha® FILLER Lidocaine established at Croma's manufacturing site 'Croma 1' ('C1') was recently implemented in addition in a new manufacturing facility (manufacturing site 'headquarter' ('HQ')). No changes were done to the finished product design or manufacturing technology or method of sterilization. The ingredients, the formulation, the packaging and the finished product specifications were not changed. The implementation of the second manufacturing site is not considered to impact the safety and effectiveness of the product.

This study will compare the IMD produced at the new manufacturing site 'HQ' with the IMD produced at 'C1' site. Therefore, each subject will randomly be assigned to one of the two IMDs ('IMD-HQ' or 'IMD-C1') at a 1:1 ratio.

Approximately 110 subjects will be included in this investigation to have 100 evaluable subjects. This sample size is considered sufficient to provide robust estimations on performance and safety parameters in the underlying overall study population as well as the IMD manufacturing site subgroups (subjects will be randomized 1:1 to IMD from either site 'C1' ('IMD-C1') or site 'HQ' ('IMD-HQ')).

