9.6 Sample Size Calculation

Confidence Interval calculation has been performed for the primary performance endpoint “The proportion of subjects ('responders') with the lip volume improved by ≥ 1 point versus baseline value at 6 weeks after initial treatment based on the investigator live assessment using a validated Lip Fullness Scale (LFS)”. A responder is defined having at least ≥ 1 grade improvement compared to baseline values on the 5 point-validate lip fullness scale”.

Approximately 110 subjects with moderate to severe volume deficiency of lips will be enrolled in order to obtain performance and safety data.

This sample size is arbitrarily selected and is considered sufficient to provide robust estimations on performance and safety parameters in the overall study population and in the subgroups regarding IMD manufacturing site. With a sample size of 100, a two-sided 95% confidence interval for a single proportion using the large sample normal approximation will extend by 0.059 in the overall population and 0.083 in the two manufacturing site subgroups from the observed proportion for an expected proportion of 0.900 (i.e., responder rate of 90%; calculated with nQuery Advanced 8.2.1.0). In order to cover subjects’ drop-out or

lost to follow-up the sample size will be increased by 10%. 110 subjects will be enrolled (with 55 subjects per manufacturing site). Thus, a robust estimation of the success rate at week 6 can be derived.

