9. Injection volume (initial and touch-up) required for an optimal augmentation of the lips with Saypha® FILLER Lidocaine

Summary of injection volume (initial and touch-up) required for an optimal augmentation of the lips by upper and lower lips will be analyzed descriptively using FAS and Safety analysis set for Overall population.

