10.8 Subgroup Analyses

Besides the ‘overall population’ (including all subjects enrolled in the investigation), which includes all enrolled subjects, the following subgroups will descriptively be analyzed:

- **IMD from manufacturing sites: ‘HQ’ and ‘C1’**
 IMD from two different manufacturing sites (‘C1’ and ‘HQ’) will be used and subjects will be randomly assigned in a 1:1 ratio to ‘IMD-C1’ or ‘IMD-HQ’, respectively.
 Subgroup analysis will compare both IMDs (‘IMD-HQ’ or ‘IMD-C1’) and separately analyze the results for the ‘IMD-C1’ and ‘IMD-HQ’ subgroups.
 Summary of subgroup analysis will compare both IMDs (‘IMD-HQ’ or ‘IMD-C1’) will be analyzed descriptively using FAS populations
- **Injection technique: ‘retrograde technique’ and ‘bolus technique’**
 Subgroup analysis will separately analyze the results for subjects treated with the two different injections techniques.
 Summary of different injections techniques will be analyzed descriptively using FAS populations
- **Injection equipment: ‘27G ½” needle’ versus cannula (‘25G x 50mm cannula’ or ‘22G x 70mm cannula’)**
 Subgroup analysis will separately analyze the results for subjects treated by means of the different injection equipment.
 All subgroup analyses are planned to be performed for the primary performance endpoint and the main secondary performance endpoints.

All subgroup analyses are planned to be performed for the primary performance endpoint and the main secondary performance endpoints using FAS population only.

The following secondary performance endpoints are planned to be analyzed:

- The percentage of responders, based on the investigator live assessment at 6, 12 and optional 18 months after the initial treatment using the validated LFS.

- The percentage of responders based on the independent photographic reviewer’s assessments before initial treatment and at Week 6, Month 6, 12 and optional Month 18 after initial treatment, based on photographs and using the validated LFS.
- The percentage of subjects with an improvement relative to baseline photographs, (subjects who have been rated as “very much improved” or “much improved” or “improved”), based on the investigator assessment at Week 6, Month 6, 12 and optional Month 18 after initial treatment using the 5-point GAIS.

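### Volume is fitted to need before Week 6, so LFS response is largely insensitive to an HQ-versus-C1 difference in effect per mL, yet injection volume is not planned by IMD

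*SAP*

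**What the plan says.** **Objective.** SAP 7.1.2 lists, as an additional objective, a comparison of the effectiveness of the filler "produced in the two different manufacturing sites". Protocol 6.1.4 goes further and sets out to demonstrate that the two IMDs do not differ in effectiveness or safety. Allocation is randomised 1:1.

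**Treatment.** Under Protocol 6.2.3 the investigator selects the volume according to the area to be corrected. Protocol 6.1 adds that an "optional touch-up treatment can be performed at Visit 2 (Week 3) in order to achieve optimal cosmetic corrections", and Protocol 6.2.4 makes this depend on the investigator judging the correction so far unsatisfactory. Protocol 6.2.1 says that IMDs from the two sites "can separately be identified and differentiated by investigator".

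**Assessment.** In Protocol Table 1 the LFS is graded at baseline and next at Week 6. There is no LFS at the Week 3 touch-up visit.

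**Analysis.** Secondary endpoint 9 is the initial and touch-up volume needed for optimal augmentation. SAP 10.6.2 item 9 says that its summary "by upper and lower lips will be analyzed descriptively using FAS and Safety analysis set for Overall population". On the by-IMD analysis, SAP 10.8 says "All subgroup analyses are planned to be performed for the primary performance endpoint and the main secondary performance endpoints using FAS population only". It then names five secondary endpoints: LFS response by the investigator, LFS response by the photographic reviewer, GAIS by the investigator, GAIS by the subject, and pain. Protocol 7.3.10 has the same five. Neither list contains volume or touch-up use. SAP 10.5 summarises the number treated and the volume, by administration and by lip, in the SAF. It does not mention IMD.

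**The concern.** When treatment is adjusted to its result, the outcome tends to be similar whatever the product, and the difference between products moves into the amount used. If one site's gel gave less lift per mL, the investigator would tend to inject more at Visit 1 or top up at Week 3, and Week 6 LFS and GAIS would look alike. The endpoint that records the amount used is the one the plan does not split by IMD.

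At stake is the HQ-versus-C1 conclusion. Similar Week 6 rates could be reported as no difference in effectiveness although one product needed clearly more gel or more repeat sessions. The question is not an idle one: Protocol 2.2 says that process parameters were adapted during the transfer and that HQ material is not CE-certified.

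**Working it through.** **1. The plan's own precision.** SAP 9.6 says that the 95% interval "will extend by 0.059 in the overall population and 0.083 in the two manufacturing site subgroups", taking a responder rate of 90%. With half-width 1.96 × √(p(1−p)/n) and p = 0.90:

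- n = 100: 1.96 × √(0.09/100) = 0.0588
- n = 50: 1.96 × √(0.09/50) = 0.0832

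Both figures reproduce.

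**2. The between-IMD contrast on Week 6 LFS, ignoring titration.** With 50 per arm and 90% in each, the half-width for the difference is 1.96 × √(2 × 0.09/50) = 0.118. Power (two-sided 5%) for 90% against 85, 80, 75 and 70% is 0.11, 0.29, 0.51 and 0.71. The contrast is imprecise before titration enters.

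**3. What titration does.** Write lift = k × volume, where k is lift per mL, and let T be the lift wanted. Complete titration gives lift = T whatever k is, and volume = T/k. If one IMD has 20% less lift per mL, the LFS difference disappears and volume rises by 1/0.8 − 1 = 25%.

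**4. Incomplete titration, by simulation.** All inputs are assumptions, because the documents give no touch-up rate and no distribution of volume:

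- wanted lift: mean 1.6 grades, SD 0.35, floor 0.8
- lift of 1.0 or 0.8 grade per mL
- initial volume: mean 95% of its aim, with relative error SD 0.15
- touch-up, making up the shortfall, when lift is below 90% of that wanted
- response: lift plus rating noise (SD 0.35) of at least 1 grade
- no upper limit on volume

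These inputs put the reference arm close to the plan's 0.900 at Week 6, after any touch-up. Each cell shows reference against weaker IMD.

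| Initial volume adapts to the product | Week 6 response | Power | Touch-up use | Power | Mean total volume (mL) | Power |
|---|---|---|---|---|---|---|
| Not at all | 0.895 vs 0.911 | 0.047 | 36.8% vs 87.8% | 1.0 | 1.64 vs 1.99 | 0.99 |
| Partly | 0.894 vs 0.901 | 0.031 | 37.0% vs 64.6% | 0.80 | 1.64 vs 2.00 | 0.99 |
| Fully | 0.895 vs 0.903 | 0.035 | 36.9% vs 36.9% | 0.025 | 1.64 vs 2.05 | 0.998 |

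With no adaptation and no touch-up, the response rates would be 0.833 against 0.669. Touch-up use shows the difference only when the initial volume has not already absorbed it. Total volume shows it in all three rows.

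**5. Volume by IMD at 50 per arm, over a range of spread.** The simulated coefficient of variation (CV) is low (0.379/1.64 = 0.23), so a wider range is needed. The half-width of the relative difference is 1.96 × CV × √(2/50) = 0.392 × CV.

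| CV (assumed) | 95% half-width | Power, 20% difference | Power, 25% difference |
|---|---|---|---|
| 0.3 | 11.8% | 0.915 | 0.986 |
| 0.4 | 15.7% | 0.705 | 0.878 |
| 0.5 | 19.6% | 0.516 | 0.705 |

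**6. Touch-up proportion at 50 per arm.** Power is 0.59 for 20% against 40%, 0.53 for 30% against 50%, and 0.34 for 30% against 45%. This measure alone is no sharper than an untitrated LFS contrast. It is worth tabulating next to volume, not in its place.

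**The case against.** The case on the other side has five parts.

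- **Masking is incomplete, and later visits are covered.** The touch-up is discretionary, and LFS response at Months 6, 12 and 18 is analysed by IMD for both the investigator and the photographic reviewer. This stands: a difference in durability could show there. Those later grades still start from titrated volumes, so volume by IMD is needed to interpret them as well.
- **Touch-up counts can be found.** Pain after touch-up is on the by-IMD list, NPRS at Visit 2 is recorded only when a touch-up is given, and SAP 9.1 includes n among its summary statistics. The n in that table is therefore the number of FAS subjects touched up per IMD, apart from missing scores. This stands too, but it is a by-product of a pain table and gives no proportion, difference or interval.
- **General wording may cover it.** SAP 9.8 says that the final analysis includes subgroups, and SAP 9.2 assigns wrongly treated SAF subjects to an IMD, which suggests that some SAF tables are by IMD. Neither names volume, and the specific text in 10.6.2 item 9 says overall population.
- **Volume is not a clean measure.** An investigator who can tell the IMDs apart chooses both volume and touch-up, so a difference could reflect expectation or habit. This stands as a limit to state with the table. The investigator's LFS grade has the same limit.
- **The study is declared non-comparative (Protocol 5.2), and listings hold the raw data.** This lowers the weight of the point. A listing is still not a planned comparison, and Protocol 6.1.4 does intend a conclusion on the two IMDs.

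**Conclusion.** The point holds in a bounded form. Week 6 LFS response is largely insensitive to an HQ-versus-C1 difference in effect per mL, and the plan's own measure of the gel required is confined to the overall population. If a 20% loss of lift per mL were made up with gel, Week 6 power would be about the false-positive level (0.03 to 0.05). The matching 25% rise in volume would be seen with power of about 0.7 to 0.99 for a CV of 0.5 down to 0.3. These sizes rest on the assumed inputs above and on volume being free to rise. A practical ceiling on volume would weaken the masking.

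A reader might infer two stronger claims that the documents do not support. One is that LFS cannot reveal any difference between the IMDs. The discretionary touch-up and the by-IMD results at Months 6, 12 and 18 rule that out. The other is that touch-up use is reported only overall. That restriction is explicit for volume, whereas for touch-up the SAP is silent and the count is indirectly available. The overall Week 6 responder estimate is not affected.

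**What to change.** In SAP 10.8, with matching wording in 10.5 and 10.6.2 item 9, add by randomised IMD:

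1. initial, touch-up and total injection volume, per lip and for both lips together;
2. the proportion of subjects given a touch-up.

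Give each with the HQ-minus-C1 difference and its 95% CI. Count touch-up volume as 0 mL where none was given, so that every FAS subject contributes and the comparison stays randomised. State that the HQ-versus-C1 LFS result is read together with these two measures, and that both follow open-label decisions and may reflect investigator expectation. Extend the endpoint list in Protocol 7.3.10, or record the addition in SAP section 11.

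The cost is a few tables. Volume per lip and touch-ups are already in the eCRF, and IMD is randomised through the same system. Sample size, visits and treatment rules do not change. The drawback for the sponsor is that the by-IMD picture may look less uniformly similar.
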